16. ARCHIVING

After finalization of the analysis, the following will be archived:

- SAP
- All computer code used in creating the analysis datasets, in generating the tables and figures, and in analyzing the data
- Tables, listings, and figures as included in the CSR
- SAS datasets

17. DEVIATION FROM THE PROTOCOL-SPECIFIED ANALYSIS

The protocol-defined secondary efficacy outcome is the time-to-first persistent clinical improvement event. To declare that clinical improvement has occurred per the language in the protocol, at least one of the following three criteria must be met:

1. Improvement by at least one WHO functional class coupled with no more than a 15% decrease from baseline in 6MWT.
2. Increase from baseline in 6MWT by at least 10% and stability or improvement in the WHO functional class.
3. Decrease from baseline in creatine kinase (a surrogate biomarker for muscle injury and inflammation) by at least 10% and no worsening in WHO functional class and no more than a 15% decrease from baseline in 6MWT.

However, a persistent improvement in estimated glomerular filtration rate (eGFR) \geq 10% of baseline was added to this criteria.

[REDACTED]

[REDACTED]

[REDACTED]

[REDACTED]

[REDACTED]

[REDACTED]

[REDACTED]

18. REFERENCES

APPENDIX A. APPROACH TO ESTIMATING MEANS AND COVARIANCE STRUCTURE USED IN THE ORIGINAL SAMPLE SIZE CALCULATIONS

A. 1. INTRODUCTION

The primary efficacy analysis will use a MMRM with the change from baseline in 6MWT as the outcome variable (Section 10.1).

[REDACTED]

- | [REDACTED]
- | [REDACTED]
- | [REDACTED]
- | [REDACTED]

[REDACTED]

- | [REDACTED]
- | [REDACTED]
- | [REDACTED]
- | [REDACTED]
- | [REDACTED]

[figure not shown]
[REDACTED]

A. 2. TREATMENT EFFECT OF BARDOXOLONE METHYL ON 6MWT

[REDACTED]

[REDACTED]

[REDACTED]

A. 3. VARIABILITY OF 6MWT IN OTHER PAH STUDIES

[REDACTED]

[REDACTED]

[REDACTED]

[REDACTED]

[REDACTED]

Figure A 2. Observed variance, covariance, and correlation in LARIAT data [REDACTED]

[figure not shown]

Table A 1. Variance-covariance and correlation structure for simulation study

[REDACTED]	[REDACTED]	[REDACTED]	[REDACTED]	[REDACTED]	[REDACTED]
[REDACTED]	[REDACTED]	[REDACTED]	[REDACTED]	[REDACTED]	[REDACTED]
[REDACTED]	[REDACTED]	[REDACTED]	[REDACTED]	[REDACTED]	[REDACTED]
[REDACTED]	[REDACTED]	[REDACTED]	[REDACTED]	[REDACTED]	[REDACTED]
[REDACTED]	[REDACTED]	[REDACTED]	[REDACTED]	[REDACTED]	[REDACTED]
[REDACTED]	[REDACTED]	[REDACTED]	[REDACTED]	[REDACTED]	[REDACTED]
[REDACTED]	[REDACTED]	[REDACTED]	[REDACTED]	[REDACTED]	[REDACTED]

A. 4. SIMULATION STUDY FOR COMPLETE DATA

[REDACTED]

- | [REDACTED]
- | [REDACTED]
- | [REDACTED]
- | [REDACTED]
- | [REDACTED]

[REDACTED]

Table A 2. Power by sample size and variance-covariance of complete data

[REDACTED]	[REDACTED]	[REDACTED]				
		[REDACTED]	[REDACTED]	[REDACTED]	[REDACTED]	[REDACTED]
[REDACTED]	[REDACTED]	[REDACTED]	[REDACTED]	[REDACTED]	[REDACTED]	[REDACTED]
[REDACTED]	[REDACTED]	[REDACTED]	[REDACTED]	[REDACTED]	[REDACTED]	[REDACTED]
[REDACTED]	[REDACTED]	[REDACTED]	[REDACTED]	[REDACTED]	[REDACTED]	[REDACTED]
[REDACTED]	[REDACTED]	[REDACTED]	[REDACTED]	[REDACTED]	[REDACTED]	[REDACTED]
[REDACTED]	[REDACTED]	[REDACTED]	[REDACTED]	[REDACTED]	[REDACTED]	[REDACTED]
[REDACTED]	[REDACTED]	[REDACTED]	[REDACTED]	[REDACTED]	[REDACTED]	[REDACTED]
[REDACTED]	[REDACTED]	[REDACTED]	[REDACTED]	[REDACTED]	[REDACTED]	[REDACTED]

5. SIMULATION STUDY WITH A MISSING DATA MODEL

[REDACTED]

[REDACTED]

Table A 3. Power by sample size and variance-covariance with a missing data model

Standard						
■	■	■	■	■	■	■
■	■	■	■	■	■	■
■	■	■	■	■	■	■
■	■	■	■	■	■	■
■	■	■	■	■	■	■
■	■	■	■	■	■	■
■	■	■	■	■	■	■
■	■	■	■			

APPENDIX B. GUIDELINES FOR RECALCULATION OF SAMPLE SIZE

B. 1. INTRODUCTION

The design of the CATALYST study is based on assumptions, as described in [Appendix A](#) of this SAP, regarding the mean trajectory of 6MWT in the treated and placebo groups and the correlation structure of the outcome. As is typical of a Phase 3 randomized clinical trial, these parameters were estimated from data that came from previous studies. Because of the uncertainty of these estimates, the protocol for the CATALYST study allows recalculation of the sample size at an intermediate point in the study. This recalculation will be based on blinded information, that is, data pooled across treatment groups. Because no unblinding will occur, recalculation will have at most a negligible impact on the Type 1 error rate for the final data analysis. See Section 2.6 for further details on blinding procedures.

The recalculation will be performed when approximately 100 patients have been randomized. At this point, relevant baseline and operational parameters will be reassessed and the study size increased if necessary to maintain desired power. A sample size re-calculation committee (SRC), composed of members from Reata and [REDACTED] will review blinded data at the time of recalculation and make a formal recommendation about study size to Reata.

The remaining sections of this Appendix summarize the current assumptions underlying the sample size and describe the planned recalculation. This appendix will have been finalized and submitted to the FDA as part of the full SAP prior to the sample size recalculation.

B. 2. STUDY DESIGN ASSUMPTIONS

As described in the protocol and in the main body of the SAP, the CATALYST study will assess efficacy based on the primary outcome, the change from baseline in 6MWT relative to placebo at Week 24. The study design calls for randomizing approximately 130 patients (65 in each group) and for assessing 6MWT at baseline and again at Weeks 4, 8, 16, and 24.

[REDACTED]

- [REDACTED]
- [REDACTED]
- [REDACTED]
- [REDACTED]
- [REDACTED]
- [REDACTED]

B. 3. RECALCULATION OF PARAMETERS

When approximately 100 patients have been randomized, a pooled dataset will be constructed with baseline and available follow-up data. Table B 1 details the original assumptions that will be checked at the time of the recalculation. At that time, [REDACTED] will rerun the sample size simulations based on the updated values for the parameters. Note that all computations will be based on the CATALYST data that is available at the time of the recalculation.

Table B 1. Tables available at time of the recalculation of parameters needed for power estimates

[REDACTED]	[REDACTED]	[REDACTED]	[REDACTED]
[REDACTED]	[REDACTED]	[REDACTED]	[REDACTED]
[REDACTED]	[REDACTED]	[REDACTED]	[REDACTED]
[REDACTED]	[REDACTED]	[REDACTED]	[REDACTED]
[REDACTED]	[REDACTED]	[REDACTED]	[REDACTED]

Figures will be provided for visual representation of data presented in the source tables.

Table B 2. Graphical presentations

Number	Title	Description
[REDACTED]	[REDACTED]	[REDACTED]

In addition to the sample size calculations noted above, the SRC will review data summaries listed in Table B 1 and Table B 2. Using all available data, the SRC will decide whether to recommend increasing the sample size up to 200.

B. 4. BLINDING PROCEDURES

All measures in place to ensure blinding to treatment assignments, as discussed in the [protocol \(Section 6.2\)](#) and this SAP (Section 2.6), will be maintained through the sample size recalculation. Specifically,

- The only individuals with access to treatment assignments will be the unblinded statistical group [REDACTED], the DSMB, and the unblinded IWRS group. No additional access to treatment codes will be granted for the sample size recalculation described in this Appendix.
- All members of the SRC as well as all patients, investigators, site personnel, laboratories, and Reata personnel (regardless of their involvement in the conduct of the study) and their designees [REDACTED] will be blinded to treatment assignments and will remain blinded until after the database is locked and formal access to the randomized treatment codes is authorized by Reata.
- The recalculation will be performed using aggregate data pooled for all patients; no treatment assignments will be provided.
- All available data for the relevant clinical parameters specified in this Appendix will be considered in recalculating sample size.
- SRC recommendations will be based on information limited to the package of data described in this Appendix.

B. 5. SRC: COMPOSITION AND LOGISTICS

The SRC will perform these evaluations and make recommendations to Reata’s senior management. The committee, which will be blinded to treatment allocation, will act by consensus. [REDACTED], its chair, will serve the SRC as the statistical representative for Reata.

The other members of the SRC will be representatives from Reata who played significant roles in developing the original sample size assumptions: [REDACTED]

After the recalculation, the SRC will provide a formal recommendation for change or no change with details and rationale to Reata’s senior management, who will make the final decision about whether to accept the recommendation. The SRC will use the attached recommendation form ([Appendix B. 7](#)) after the recalculation.

Should the SRC and Reata’s senior management agree that a sample size increase is warranted after the recalculation, Reata will document the increase in a note to file to the clinical sites and, as needed, to the EC/IRB/REB and the DSMB. If a change in sample size is implemented, a protocol amendment will not be required because the current protocol includes a provision for the sample size recalculation.

B. 6. CALCULATIONS AND DATA SUMMARIES

████████████████████ will provide the SRC with the set of predefined tables and figures presented in Table B 1 and Table B 2.

The SRC will review the materials and provide ██████████ with updated assumptions for the recalculations. ██████ will detail the updated assumptions, methodology, and document results of the sample size and event recalculations documented in a report provided to the SRC and ultimately to Reata’s senior management.

B. 7. RECOMMENDATION FORM

CATALYST Trial Sample-size Recalculation Committee (SRC) Recommendation Report

Meeting Date: _____

Sample Size Recalculation

Meeting Attendees:

The SRC charged with the review of sample size for the CATALYST Trial reviewed data summaries dated [_____].

As a result, the SRC recommendation is:

- To continue the trial unmodified.
- To continue the trial and amend the study design as checked:
- To increase sample size to [_____] due to:
 - higher variability than expected
 - higher rate of drop-outs than expected
 - lower correlation than expected
 - faster enrollment and limited ability to test assumptions

Comments:

 (SRC Chair) Date

APPENDIX C. SCHEDULE OF ASSESSMENTS

The schedule of assessments is available in the protocol.

APPENDIX D. CLASSIFICATION OF VISITS

Table D 1. Classification of on treatment visits

Timing of assessment (days relative to first dose of study drug ^a)	Target day	Visit associated with assessment
1	1	Day 1 ^a
2 to 10	7	Week 1
11 to 21	14	Week 2
22 to 35	28	Week 4
36 to 49	42	Week 6
50 to 84	56	Week 8
85 to 139	112	Week 16
140 to 182	168	Week 24 ^a
7 ≤ Days after last dose ≤ 35	28	Week 28 ^c

^a Day 1 is the day of first dose of study drug.

^b Week 24 values is the average of the two values closest to target date.

^c Week 28 is only applicable to eGFR change from baseline efficacy analysis

Table D 2: Analysis Visits for Post-Treatment Safety Analysis

Analysis Visit	Label	Target Study Day (Reference Day is Days After Last Dose)	Analysis Window
40	4-weeks – Off Treatment	28	$7 \leq \text{Study Day} \leq 35$
80	8-weeks – Off Treatment	56	$36 \leq \text{Study Day} \leq 63$
120	12-weeks– Off Treatment	84	$64 \leq \text{Study Day} \leq 91$
240	24-weeks– Off Treatment	168	$92 \leq \text{Study Day} \leq 175$

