7. INVESTIGATIONAL PLAN

7.1. Overall Study Design

This double-blind, randomized, placebo-controlled trial will study the safety, tolerability, and efficacy of bardoxolone methyl in qualified patients with WHO Group I CTD-PAH.

Qualified patients will be randomized 1:1 to either bardoxolone methyl or placebo to be administered once daily for 24 weeks. Patients randomized to placebo will remain on placebo throughout the study and undergo sham titration. Patients randomized to bardoxolone methyl will start at 5 mg and will dose-escalate to 10 mg at Week 4, unless contraindicated clinically. Dose de-escalation is permitted during the study if indicated clinically. Please refer to [Section 7.3.1](#) for additional details on dose escalation and dose de-escalation.

All patients in the study will follow the same visit and assessment schedule. Following randomization, patients will be scheduled to be assessed in person during treatment at Weeks 1, 2, 4, 6, 8, 16, and 24 and by telephone contact on Days 3, 10, 21, 31, 38, 84, and 140. Patients will also be scheduled to be assessed at an in-person follow up visit at Week 28, four weeks after the end of treatment.

Patients who complete the study and are treatment-compliant to their assigned dose will be eligible for a separate open-label extension study.

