5.2.1. Laboratory parameters

Post-baseline laboratory measurements are defined as the scheduled or unscheduled measurements collected closest to (or on) the patient’s target visit day ([Appendix D](#)), with collection date identified in the central laboratory data. If two assessments are equidistant from a

target study day, the earlier assessment is used. If the visit used for analysis includes two assessments on the same day, the average of the two measurements will be used. As with the baseline retest convention, if both the original and a retest result for a scheduled post-baseline laboratory are available in the central laboratory data, the original result will be used and the second (i.e., ‘retested’) result will be ignored. Otherwise, if the original result is not available (e.g., central laboratory detects an error) but a retest result is available, the retested result will be used as the scheduled post-baseline measurement.

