12. SAFETY ANALYSES

12.1. Safety variables

Safety variables will include physical examinations, vital sign measurements, ECG, clinical laboratory measurements, concomitant medications, AEs, and SAEs. The safety analyses will include all results collected from randomization through the end of the study. The safety analyses will include only patients in the safety population, with patients classified by whether they received any dose of bardoxolone methyl or not. For laboratory data, vital signs, and ECG data, On-treatment values will be summarized according to the analysis study windows and off-treatment values will be summarized according to the analysis study windows in [Appendix D](#).

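### The 24-week off-treatment row of SAP Table D 2 opens at Day 92 after last dose, so values from 13 to 18 weeks off drug can be reported as 24 weeks

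*SAP*

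**What the plan says.** Table D 2 in SAP Appendix D defines the analysis visits for post-treatment safety. Its time axis is stated in the column heading: "Target Study Day (Reference Day is Days After Last Dose". The four rows are:

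| Row | Target day | Window (days after last dose) |
|---|---|---|
| 4 weeks | 28 | 7 to 35 |
| 8 weeks | 56 | 36 to 63 |
| "12-weeks– Off Treatment" | 84 | "64 \leq \text{Study Day} \leq 91" |
| "24-weeks– Off Treatment" | 168 | "92 \leq \text{Study Day} \leq 175" |

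There is no 16- or 20-week row.

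SAP Section 12.1 applies the table to laboratory, vital-sign and ECG data: "off-treatment values will be summarized according to the analysis study windows in" Appendix D. When a window holds more than one value, Section 5.2.1 picks by distance from the target: "Post-baseline laboratory measurements are defined as the scheduled or unscheduled measurements collected closest to (or on) the" target day. Section 5.2.2 has the same rule for other parameters, and ties go to the earlier value.

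Patients who stop drug early are asked to stay for all scheduled assessments if possible (Protocol Section 8.4.1, SAP Section 2.2.2). The last planned contact is the "in-person follow up visit at Week 28, four weeks after the end of treatment" (Protocol Section 7.1). Protocol Table 3 places Week 24 at Day 168 and Week 28 at Day 196, each within 3 days.

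**The concern.** The rows at 8 and 12 weeks each end 7 days after their target, and the next row starts the following day. That is workable while targets are 28 days apart. Between 12 and 24 weeks the gap is 84 days, and the same construction makes the last row absorb everything from Day 92 on. A value at Day 92 is 8 days from the 12-week target and 76 days from the 24-week target, yet it carries the 24-week label.

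These summaries exist to show whether a change in a laboratory value, vital sign or ECG measure has gone or remains after drug is stopped. A reader will take the last row as the state at about 24 weeks. If it is filled by values from 13 to 18 weeks, the label misstates how long recovery has been observed. If stopping times differ between the arms, the same label would also cover different times off drug in each arm.

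**Working it through.** **1. The table as printed.** Targets are 7 × weeks: 28, 56, 84 and 168, which agree for all four rows. Window lengths are:

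- 8 weeks: 63 − 36 + 1 = 28 days, from 20 below target to 7 above.
- 12 weeks: 91 − 64 + 1 = 28 days, from 20 below to 7 above.
- 24 weeks: 175 − 92 + 1 = 84 days, from 76 below to 7 above.

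**2. Days in the 24-week row that are nearer 12 weeks.** Day d is nearer 84 than 168 when d − 84 < 168 − d, that is d < 126. Within the window these are Days 92 to 125: 34 of 84 days = 40.5%. Day 126 is the tie. For comparison, the 8-week row has Days 36 to 41 nearer the previous target and the 12-week row has Days 64 to 69: 6 of 28 = 21.4% in each.

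**3. The on-treatment table.** Table D 1, in the same appendix, sets its interior edges at or within a day of the midpoints. For targets 56 and 112 the midpoint is 84 and the edge is 84/85; for 112 and 168 the midpoint is 140 and the edge is 139/140. The corresponding midpoint for 84 and 168 is 126; Table D 2 uses 91/92.

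**4. The trial's own visits.** SAP Section 5.4 defines days since last dose as visit date minus date of last dose. With last dose on Day L and nominal visits, Week 24 is at 168 − L and Week 28 at 196 − L.

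- Week 28 falls on Days 92 to 125 off drug when L is 71 to 104 (196 − 104 = 92; 196 − 71 = 125). In weeks, 92/7 = 13.1 and 125/7 = 17.9.
- For L = 71 to 76, Week 24 (97 to 92 days off) is in the same row, but Week 28 (125 to 120) is closer to 168 and is selected.
- For L = 77 to 104, Week 28 (119 to 92 days off) is the only scheduled value in the row.

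So for every nominal L from 71 to 104, the 24-week row receives a value that is nearer the 12-week target.

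**5. Two visits, two labels.** For L = 77 to 104, Week 24 is 91 to 64 days off drug, which is inside the 12-week window. If Week 24 is classified by last dose, the two visits are 28 days apart but appear under labels 168 − 84 = 84 days apart.

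**6. Earlier stops.** Still classifying by last dose and taking the value closest to 168:

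- L = 1 to 20: Week 24 at 167 to 148 days off (Week 28, at 195 to 176, lies beyond the window).
- L = 21 to 56: Week 28 at 175 to 140 days off.
- Over these 56 stop days, none gives a value nearer 84, the median is 157.5 days, and 36 (L = 1 to 14 and 21 to 42) are within 14 days of 168: 36/56 = 64%.
- L = 57 to 70: Week 28 at 139 to 126 days off, not nearer 84 but 29 to 42 days short of 168.

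These are counts of possible stop days, not forecasts of patients.

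**The case against.** **SAP Section 5.2.3 can be read against the two-visit example.** It classifies assessments through Week 24 by time from randomization, whatever the patient's drug status, and sends early stoppers who remain in follow-up to the rules of Sections 5.2.1 and 5.2.2. On that reading, the Week 24 visit of a patient who stopped on Days 77 to 104 is simply Week 24 and never enters the 12-week row. Section 12.1, and the sentence in 5.2.3 that classifies post-treatment assessments by last dose, point the other way. This objection stands: the two-visit result is conditional. The Week 28 result does not depend on it, because Week 28 comes after Week 24 and is classified by last dose on either reading.

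**The selection rule and early stopping limit the damage.** The protocol describes effects that come early: fluid overload in the first three to four weeks (Section 5.1.2), transaminase peaks two to four weeks after starting or raising the dose (5.1.3), and muscle spasms mostly in the first two months (5.1.4). If stops cluster there, the row is mostly well labelled. This stands as a limit on size. The rule cannot help for stops on Days 71 to 104, since no scheduled visit follows Week 28. An unscheduled value would bring the row closer to target only if taken after Week 28, and the 3-day visit windows shift the edges by only a few days.

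**Few outputs use these rows.** Off-treatment adverse events follow a 30-day rule (SAP 12.2), transaminase thresholds are counted at any time in the study (12.3.1), worst-case shift tables use all results (12.3.3), and listings show every measurement (5.2). This stands. It is also argued that labelling an earlier value as 24 weeks overstates persistence and so errs towards caution. That holds only if recovery is steady, which the documents do not establish.

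**Conclusion.** The window is misplaced. Forty percent of its days (34 of 84) are nearer the 12-week target, and patients who stop on Days 71 to 104 and attend Week 28 will have a 13- to 18-week value reported as 24 weeks. This rests on nominal visit days and on patients staying in the study after stopping drug. For stops on Days 77 to 104, the appearance of visits 28 days apart as 12 and 24 weeks further requires that Week 24 be classified by last dose, which the SAP leaves open.

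Three stronger readings are not supported:

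- A reader might turn the day count into a share of patients or values mislabelled. Counting stop days equally gives 34 of the 104 that can fill the row (33%), but the documents give no distribution of stopping times, so equal weighting has no basis.
- A reader might infer that the speed of recovery will be misreported by a factor of three. That needs the contested reading of Section 5.2.3, and the visible text plans no analysis of recovery rate from these rows.
- A reader might try to state how much residual effect is overstated. The documents give no rate of recovery after stopping, so this cannot be computed.

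The effect is confined to descriptive off-treatment summaries by visit. The primary 6MWT analysis is untouched. The point is worth correcting because the error follows from applying the rule as written and is easy to remove.

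**What to change.** Replace the 92-to-175 row with three rows and move the upper edge of the 12-week row, so that the edges fall at the midpoints:

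| Row | Target | Window | Upper edge |
|---|---|---|---|
| 12 weeks | 84 | 64 to 98 | (84 + 112)/2 = 98 |
| 16 weeks | 112 | 99 to 126 | (112 + 140)/2 = 126 |
| 20 weeks | 140 | 127 to 154 | (140 + 168)/2 = 154 |
| 24 weeks | 168 | 155 to 175 | unchanged |

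Print the median and range of actual days since last dose under each row. Reconcile Sections 5.2.3 and 12.1, stating whether a visit after last dose but at or before Week 24 is classified by randomization, by last dose, or in both sets of tables.

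The cost is an edit to one SAP table, a clarifying sentence and the programming. No new data are needed. Counts per row become smaller. Where a window holds two values from one patient, only the one closest to target is kept. If visits are classified by last dose, this happens in the widened 12-week row for stops on Days 98 to 104 (Week 24 at 70 to 64 days, Week 28 at 98 to 92).

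Merely moving the 12/24-week boundary to Day 126/127 is a weaker repair. On the same reading it puts both visits of every patient who stops on Days 77 to 104 (64 to 91 and 92 to 119 days) into the 12-week row, and one of the two is dropped.
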